**Amended: 12/27/11**

Memorial Sloan-Kettering Cancer Center  
IRB Protocol

IRB#: 09-060 A(4)

microvessel density (CD31) will be applied to FFPE sections. Serial sections will be reviewed by an experienced neuropathologist. Ki-67 staining will be evaluated and a score designated indicating the percentage of positively stained tumor cells per quartile of tumor tissue. All cells with nuclei staining of any intensity will be defined as positive. The proliferative activity score, quantified as the percentage of MIB-1 stained nuclei per total nuclei in the sample, will be estimated from a representative slide selected by the neuropathologist. For MVD assessment using CD31, tumor sections will be scanned at low magnification (x40) to identify the region of the section with the highest microvessel density. This area will be counted at a magnification of x200 for CD31-positive expression, and the proportion of CD31-positive cells computed for all specimens.

Histologic findings at a given biopsy site will be compared with ROI analyses at the same location on the co-registered PET-MRI studies. Pharmacokinetic modeling will be applied to these ROI measurements in order to generate parametric maps reflecting the proliferation rate constant,  $k_3$ , and  $K_{trans}$  (microvascular permeability). Estimated parameter values will be correlated with the presence of molecular markers (MIB-1, CD31), and compared with imaging features at the prospectively defined biopsy sites.

Secondary Aim #1 Study Design: The objective will be to investigate the feasibility of applying a novel imaging software platform to the measured dynamic brain PET imaging data. Voxel-based parameter estimates will be generated using ROIs selected for targeted biopsy and, in turn, utilized to construct parametric images (maps) reflecting the spatial distribution of the rate of  $^{18}\text{F}$ -FLT cellular trapping (or proliferation). These estimates will be compared with kinetic parameters determined using traditional ROI-based pharmacokinetic modeling methods. As input to the model, venous time-activity curves will be derived non-invasively at the level of the confluence of the sagittal, straight, and transverse sinuses, and corrected for hematocrit and partial volume effects.

Venous input functions will be generated using previously described protocols. We will use a summed image of the first 2 frames (1 min) of the study and place small ROIs (5 mm) on two to five successive planes in the image at the level of the confluence of the superior sagittal, transverse, and straight sinus, covering a total axial depth of 1.0-1.5 cm. The co-registered MRI and PET-CT will be used to confirm our interpretation of the vascular anatomy revealed by PET and to verify the position of the ROIs. In addition, threshold values of 50% of the peak activity in the sinuses will be used for further guiding the placement of the ROIs, with data for the ROIs on successive planes averaged. The resulting time course of the SUV will be automatically corrected for detection efficiency, scatter attenuation, and decay. In order to correct for partial volume averaging effects, the transverse dimension of the confluence of sinuses will be measured on axial T2-weighted imaging. Using the PET system recovery coefficient, derived from phantom studies as a function of the source dimension, a recovery coefficient for the confluence of sinuses will be determined. Each TAC data point will be divided by this recovery coefficient to yield the corrected TAC data.

Venous input functions will be compared with non-invasively derived arterial input functions, the latter determined from the internal carotid arteries at the level of the skull base on PET after fusing with MR images for artery identification. The feasibility of using arterial structures at this level will be investigated using the same method described above for determining venous input functions. The agreement of kinetic parameter values calculated using both venous and arterial input functions will be examined.

## Memorial Sloan-Kettering Cancer Center IRB Protocol

**IRB#: 09-060 A(4)**

A number of studies have compared rate constants estimated using non-invasive, image-based input functions *versus* time-activity curves (TACs) generated from sampled arteries or arterialized veins, and have found no statistically significant differences for rate constants obtained with these input functions. More recently, *image-derived* input functions for transverse and cavernous sinuses have been used in conjunction with compartmental modeling to investigate the kinetic behavior of *malignant brain tumors*, with the resulting rate constants found to adequately describe F-FLT uptake characteristics. Thus, as the collective results of these studies have demonstrated no statistically significant differences between blood samples and tomographically obtained input functions in terms of the kinetic parameters estimated, it is not essential that blood samples be acquired for determining an input function. However, up to 4 blood samples (approximately 3-milliliter per sample) may be taken post-injection, within the 1 hr imaging time period (i.e., roughly 15, 30, 45, and 60 min), for calibrating the corresponding image-based FLT TAC and/or improving pharmacokinetic parameter estimates, as well as for test consistency. It should be noted that a range of post-injection time points (ultimately defining the blood TAC) can be selected for blood draws, as estimated pharmacokinetic parameters will not be critically dependent on the exact times chosen. This procedure will be performed in a number of patients to establish whether there is a relatively constant calibration factor or improved pharmacokinetic data that can be derived, which in turn would be applied to all the remaining patient data analyzed.

Secondary Aim #2 Study Design: Voxel-wise parameter estimates derived in secondary aim #1 will be compared with static measures of F-FLT uptake using ROIs selected for targeted biopsy. To obtain static F-FLT images, data will be summed between 30 and 60 minutes post-injection. Estimated parameter values will be correlated with the proliferative activity score or the percentage of MIB-1 stained nuclei per total nuclei in the sample as described under the Primary Aim Study Design.

Exploratory Aim Study Design: Biopsy samples will be acquired from regions of increased/decreased proliferative activity (FLT uptake). Gene expression from microdissected portions will be assayed by Affymetrix U133Plus2 arrays. Differential gene expression signatures will be derived for each pair of samples in a resection, representing differences between FLT uptake values. Signatures will be compared across samples to attempt to characterize a core signature. Core signatures will be investigated by comparison to known transcriptome signatures of molecular subclasses of GBM as well as compared with other pathways and signatures.

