## 2.0 OBJECTIVES AND SCIENTIFIC AIMS

Primary Aim: To investigate relationships between voxel-based determinations of proliferation rate and observed MR imaging features (i.e.,  $K_{trans}$  or microvascular permeability; fBV, tissue fractional blood volume), as well as with spatially registered histologic measures of tumor cell proliferation (Ki67) and microvascular density (CD31) at corresponding locations.

Secondary Aim #1: To attempt to corroborate voxel-based parameter estimates reflecting tumor cell proliferation with estimates derived using standard ROI-based pharmacokinetic modeling methods, for improving the characterization of high-grade gliomas using dynamic  $^{18}\text{F}$ -FLT PET-CT.

Secondary Aim #2: To assess whether static measures of  $^{18}\text{F}$ -FLT uptake can adequately serve as non-invasive biomarkers of proliferative activity or whether parametric images, based on compartmental analyses of the FLT pharmacokinetics, are required by correlating findings of both approaches with regional histologic assays of tumor cell proliferation.

Exploratory Aim: To evaluate whether differences in gene expression seen between areas of increased and decreased proliferative activity on parametric maps define consistent differential transcriptome signatures for comparison with known molecular subclasses of GBM and known pathways.

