### 3.3 $^{18}\text{F}$ -FLT Tracer Kinetic Modeling:

The utility of static (SUV) versus dynamic measures (i.e.,  $k_3$ ) of  $^{18}\text{F}$ -FLT PET as an imaging biomarker represents different schools of thought, with examples of both found in the literature, and without a clear consensus offered. Static measures of brain tumor  $^{18}\text{F}$ -FLT uptake at various times post-injection have been shown to correlate with histopathologic proliferation markers (Ki-67) in patient studies. More recently, measured FLT SUV values were used to assess treatment response in recurrent malignant gliomas. However, it is not clear what the FLT SUV measurements in such studies reflect, as both changes in tracer delivery and/or metabolic trapping will contribute to net tracer uptake. As an alternative approach, several previous clinical investigations have assessed uptake in brain tumors dynamically, generally using ROIs having maximum proliferative activity, in conjunction with two-tissue compartment (four-rate constant) models, in order to estimate kinetic rate constants reflecting tracer transport and cellular proliferation. Both methods continue to be utilized for in vivo brain tumor applications, noting that recently recommended  $^{18}\text{F}$ -FLT data acquisition and analysis techniques have included static PET imaging at 40-60 min and corresponding SUV measurements of tumor activity concentration for brain tumors.

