
Primary Aim Study Design: Preoperative anatomical MRI images will be uploaded to the BrainLAB VectorVision® neuronavigation system, a frameless stereotaxy and image-guided surgical navigation system integrated with the Intraoperative MRI suite. Planned resection volume will be contoured by the neurosurgeon conventionally, based on the anatomic MRI.  $^{18}\text{F}$ -FLT PET-MRI studies will then be uploaded and registered by a radiologist. For each patient undergoing resection, up to four prescribed ROIs within the planned resection volume will be selected for potential targeted biopsy based on concordance/discordance or heterogeneity of PET and MRI imaging characteristics (i.e., increased  $^{18}\text{F}$ -FLT uptake/MRI-enhancing; increased  $^{18}\text{F}$ -FLT uptake/MRI-non-enhancing; low  $^{18}\text{F}$ -FLT uptake/MRI-enhancing; increased  $^{18}\text{F}$ -FLT uptake/MRI-nonenhancing). ROIs will be no smaller than a cubic centimeter. The operative plan, in terms of the tumor resection volume, will not be guided by decisions regarding sites of potential biopsy selected on the co-registered FLT PET-MRI study. It is expected that

IRB  
PB

Amended: 12/27/11

**Memorial Sloan-Kettering Cancer Center  
IRB Protocol**

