  - The  $^{18}\text{F}$ -FLT PET-CT and baseline MRI studies will be uploaded onto BrainLab 1 and co-registered by the neuroradiologist using Vector-Vision® cranial navigation software. This will not be done in the operating room. The PET and MR image sets will be co-registered by applying the 3D rigid transformation (translations/rotations) to the PET image set, which aligns the CT image set of the PET-CT study and the MR image set.
  - The operating neurosurgeon will be blinded to the pre-operative PET study, and planned tumor resection volume will be pre-determined solely on the basis of anatomic MRI per routine. Preoperative MRI images will be uploaded to the BrainLAB VectorVision® neuronavigation

Memorial Sloan-Kettering Cancer Center  
IRB Protocol

IRB#: 09-060 A(4)

system, a frameless stereotaxy and image-guided surgical navigation system integrated with the Intraoperative MRI suite.

- On co-registered PET-MRI scans and prior to surgical resection, up to four prescribed ROIs within the planned resection volume will be marked for potential targeted biopsy by two neuroradiologists and a nuclear medicine attending, blinded to the surgical planning. These ROIs will be selected based on heterogeneity of PET and MRI imaging characteristics (e.g., high  $^{18}\text{F}$ -FLT uptake/no enhancement; low  $^{18}\text{F}$ -FLT uptake/enhancement). Fused images containing the marked biopsy sites will be uploaded to the BrainLAB VectorVision® neuronavigation system for viewing by the neurosurgeon in the operating room. As noted above, however, the operative plan, in terms of the tumor resection volume, will not be guided by decisions regarding sites of potential biopsy selected on the co-registered FLT PET-MRI study.
- ROI analyses for determination of tracer uptake measurements and the generation of time-activity curves for blood and tumor will be performed on an AW Workstation (GE Healthcare) that runs the Voxulus™ software module for voxel-based pharmacokinetic modeling. Voxel-based pharmacokinetic modeling, traditional ROI-based pharmacokinetic modeling (*SAAM II* program), and static uptake determinations will all be performed on this workstation. The information derived from these analyses will not be used for surgical planning or uploaded for use in the operating room.

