**IRB#: 09-060 A(4)**

number of samples from each tumor that represent differential features. For larger sample sets, simple Venn intersection may reveal core signature genes. Sparser samplings of feature contrasts will be analyzed by pairwise Gene Set Enrichment to identify a subset of mutually expressed signature genes.

Analysis of gene signatures: Gene signatures representing contrasting imaging features will be compared with known signatures representing previously described molecular subclasses of GBM, including the "Proneural", "Proliferative" and "Mesenchymal" classes, as well as molecular subclasses already emergent in the analysis of 206 GBM samples in The Cancer Genome Atlas pilot project to date. Signatures will be compared by GSEA and gene ontology. GSEA will also be used to analyze feature-derived signatures in an exploratory process to characterize possible enrichment for altered expression within canonical pathways. The Connectivity Map offers another potentially valuable resource for mining feature-derived signatures, and can be approached with specific hypothesis: that differential proliferation and permeability, as image-derived features, may be associated with transcriptome evidence of PI3 kinase signaling or VEGF signaling, both of which are well represented in the database. Analysis will include exclusion of gene subsets such as cell cycle members whose differential regulation is likely to correlate with simple histologic measures of proliferation.

For the exploratory aim, we can evaluate the power we will have to detect a difference in gene expression levels between areas of high and low tracer uptake (or signal intensity) within an individual. With 15 subjects contributing a sample from both a high and low uptake area, we expect to be able to detect a twofold difference in base 2 log intensity levels with a Type I error of 0.001 and a Type II error of 0.05 if the standard deviation for the expression levels is 0.75 (using base 2 logarithms) or less. A standard deviation of 0.75 is within the range of what we expect to see.

Sample size justification:

For this pilot study, we expect there to be 15 eligible patients per year, and we will aim to reasonably accrue 8 of these patients per year for two years.

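### Expression pairs are contrasted on FLT uptake alone, although sites are picked on FLT and MRI enhancement jointly, so enhancement-related genes can enter the proliferation signature

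*Combined protocol and SAP*

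**What the plan says.** **Site selection.** In Section 4.2 (Primary Aim Study Design), up to four regions per patient are "selected for potential targeted biopsy based on concordance/discordance or heterogeneity of PET and MRI imaging characteristics". The patterns printed there are increased FLT/enhancing, increased FLT/non-enhancing and low FLT/enhancing. The fourth entry repeats increased FLT/non-enhancing, so low FLT/non-enhancing does not appear. Section 4.3 (PET scan protocol) says "These ROIs will be selected based on heterogeneity of PET and MRI imaging characteristics" and gives two examples: high FLT without enhancement, and low FLT with enhancement.

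**Contrast.** The aim in Section 2.0 concerns "differences in gene expression seen between areas of increased and decreased proliferative activity on parametric maps". The Exploratory Aim Study Design in Section 4.2 makes this operational through uptake: "Differential gene expression signatures will be derived for each pair of samples in a resection, representing differences between FLT uptake values". Section 3.3 notes, for static uptake, that "both changes in tracer delivery and/or metabolic trapping will contribute to net tracer uptake".

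**Analysis.** Section 11.0 tests paired samples with SAM and then looks for core genes shared across tumours, by Venn intersection or pairwise gene set enrichment. It refers to imaging features in general and states a hypothesis "that differential proliferation and permeability, as image-derived features, may be associated with transcriptome evidence of PI3 kinase signaling or VEGF signaling". It sets aside subsets such as cell-cycle genes. It has no same-enhancement matching, no enhancement or Ktrans term and no separate permeability contrast.

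**The concern.** Pairing within a patient removes patient-level differences. It does not remove a second feature that differs between the two sites. If the high-FLT sample is non-enhancing and the low-FLT sample is enhancing, their expression difference carries both features, and the plan attributes all of it to FLT. Labelling the pairs by k3 instead of uptake would not cure this, because the same two sites would still differ in enhancement.

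Two errors follow for such pairs. A gene that responds only to enhancement appears in the proliferation signature with its sign reversed. A gene that rises with both features is pulled towards zero and can be missed. Section 11.0 treats proliferation and permeability as distinct features linked to PI3 kinase or VEGF signalling, and that distinction is what is lost. The plan expects two observations per patient on average, so many patients will supply a single pair and the features cannot be separated within that patient afterwards. Tissue cannot be re-sampled after resection.

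**Working it through.** **Inputs from Section 11.0.** 15 within-patient pairs; twofold difference, taken as δ = 1 log2 unit; Type I error 0.001 (two-sided assumed); Type II error 0.05; SD 0.75.

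**The plan's own figure.** Taking 0.75 as the SD of the within-pair difference and using the normal approximation:

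n = [(3.291 + 1.645) × 0.75 / 1]² = 13.7, so 14 pairs against 15 planned. Power at 15 pairs = Φ(√15/0.75 − 3.291) = Φ(1.87) = 0.97, consistent with the stated 95%.

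An exact paired t-test gives 0.81 on the same inputs. If 0.75 were instead the per-sample SD with no within-patient correlation, the SD of the difference would be 0.75√2 = 1.06 and power 0.64 (normal) or 0.37 (t). The first reading is kept below, with results as t / normal.

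**Assumptions not in the documents.** The enhancement effect is set to 1 log2 unit, borrowed from the FLT effect. The number m of pairs that also differ in enhancement is varied from 0 to 15.

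**Model.** For pair i, d_i = β_F + β_E·e_i + error, where e_i is the enhancement difference, high-FLT site minus low-FLT site (−1, 0 or +1). For the Section 4.3 example pair, e_i = −1. An enhancement-only gene (β_F = 0, β_E = 1) with m pairs mismatched that way has expected mean contrast −m/15.

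Simulated probability of a call at 0.001 in the unadjusted contrast, and power for a true FLT gene once e_i is in the model:

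| m of 15, one direction | Mean contrast | Enhancement-only gene called (t / normal) | Adjusted power, true FLT gene (t / normal) |
|---|---|---|---|
| 15 | −1.00 | 0.81 / 0.97 | not estimable |
| 12 | −0.80 | 0.35 / 0.80 | 0.08 / 0.16 |
| 10 | −0.67 | 0.14 / 0.56 | 0.18 / 0.38 |
| 8 | −0.53 | 0.05 / 0.29 | 0.32 / 0.59 |
| 5 | −0.33 | 0.009 / 0.058 | 0.53 / 0.82 |
| 3 | −0.20 | 0.002 / 0.012 | 0.65 / 0.91 |
| 0 | 0 | 0.001 / 0.001 | no adjustment needed: 0.81 / 0.97 |

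With e_i in the model, the enhancement-only gene is called at about 0.001 wherever the model can be fitted.

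**Mixed directions.** If all 15 pairs are mismatched but 12 one way and 3 the other, the unadjusted rate is 0.015 / 0.42; at 8 against 7 it is <0.001 / 0.002. If high/low pairs are drawn evenly from a full two-by-two of FLT and enhancement (half matched, a quarter each way), the t-test rate is 0.1% at 0.001 and 5% at 0.05, which is nominal.

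**Cancellation.** A gene with β_F = β_E = 1 has mean contrast 1 − m/15. The t-test detects it in 0.1% of studies at m = 15 and about 3% at m = 8, against 81% at m = 0.

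**Direction as printed.** Low FLT is listed only with enhancement. Among the listed patterns, the only mismatched high/low pair is therefore increased/non-enhancing against low/enhancing, which always gives e_i = −1. The only matched pair is increased/enhancing against low/enhancing.

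**The case against.** A reader might infer that an enhancement gene enters the signature as easily as a true proliferation gene, or that every pair differs in both features. The documents support neither. The first needs all 15 pairs mismatched in one direction with an enhancement effect as large as the FLT effect. On the second, Section 4.3 introduces its two patterns only as examples, and the Section 4.2 list contains an enhancing high/low pair that differs in FLT alone. If the repeated fourth entry is a misprint for low/non-enhancing, the list is a full two-by-two, and an even draw from it gives no net inflation.

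The simulated test is also not the planned one. SAM is followed by a search for genes common across tumours, and a gene that differs in only a minority of pairs is less likely to survive an intersection. Section 11.0 speaks of imaging features in the plural and names permeability, so the plan is not blind to the second feature. The primary aim also compares Ktrans with each FLT parameter, so overlap between the two would be visible.

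These points limit the size and stand to that extent. They do not close the gap. Nothing in the plan makes mismatches balance, the printed list pushes them one way, and naming permeability in a later hypothesis does not separate it within the contrast. The cell-cycle exclusion may drop genuine proliferation genes, while no exclusion is stated for vascular or permeability genes.

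The objection that restricting the contrast to same-class pairs would waste data also stands, and the fix respects it.

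**Conclusion.** The point holds in a limited form. Sites are selected on two features, the signature is defined by one, and nothing separates them. Enhancement-related genes can therefore be labelled as proliferation genes, and genes that rise with both can be lost.

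The size cannot be fixed from the documents. The share of mismatched pairs, their direction and the enhancement effect are all assumptions, and the SAM and core-gene steps are not modelled. Under the stated assumptions and a t-test, the rate runs from nominal (matched or balanced pairs), through about 1% at 5 of 15 and about 5% at 8 of 15, to 81% in the extreme case.

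A reader might take this as a threat to the trial's main conclusions. It is not: Section 11.0 calls all analyses exploratory, and what is at risk is the labelling of a hypothesis-generating signature. The priority is minor to moderate. It is worth acting on because the remedy is cheap and the site-selection part cannot be applied after surgery.

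**What to change.** 1. **Site selection (Sections 4.2 and 4.3).** Within the existing limit of four regions and the pre-set resection volume, ask the readers to include one high/low FLT pair of the same enhancement class wherever the tumour offers it. Correct or confirm the repeated fourth pattern.
2. **Analysis (Exploratory Aim Study Design in Section 4.2; Section 11.0).** Keep all pairs in the planned analysis. Add a gene-wise within-patient analysis with both the PET term and the enhancement or Ktrans difference, or a sensitivity analysis on same-class pairs. When all mismatches run one way, the two give the same FLT estimate, but the same-class subset has fewer residual degrees of freedom (6 against 13 when 8 of 15 are mismatched).
3. **Reporting.** State how many pairs differ in enhancement and in which direction. Report the permeability signature from its own term. Call a gene proliferation-related only if it persists after adjustment.

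**Cost.** No extra sites or arrays are needed. The adjusted analysis loses power: t-power is about 0.32 if 8 of 15 pairs are mismatched in one direction, and the FLT term is not estimable if all are, which is why site selection has to change first. Some region slots would go to same-class pairs instead of the widest PET/MRI contrast, which also serves the primary aim.
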